13.1 Monitoring

13.1.1 Monitoring of the Study

The clinical monitor, as a representative of the sponsor, has the obligation to closely follow the study. In doing so, the monitor will visit the investigator and study site at periodic intervals, in addition to maintaining necessary telephone and letter contact. The monitor will maintain current personal knowledge of the study through observation, review of study records and source documentation, and discussion of the conduct of the study with the investigator and personnel.

All aspects of the study will be carefully monitored, by the sponsor or its designee, for compliance with applicable government regulation with respect to current GCP and current standard operating procedures.

13.1.2 Inspection of Records

Investigators and institutions involved in the study will permit study-related monitoring, audits, IRB/IEC/IBC review, and regulatory inspections by providing direct access to all study records. In the event of either an audit or inspection, the investigator agrees to allow the sponsor, representatives of the sponsor, or a regulatory agency (eg, FDA or other regulatory agency) access to all study records.

The investigator should promptly notify the clinical research associate (CRA) of any audits or inspections scheduled by any regulatory authorities and promptly forward copies of any reports received to the CRA. The CRA will then inform and forward any reports to the sponsor.

13.2 Management of Protocol Amendments and Deviations

13.2.1 Modification of the Protocol

Any changes in this research activity, except those necessary to remove an apparent, immediate hazard to the subject, must be reviewed and approved by the sponsor or its designee. Amendments to the protocol must be submitted in writing to the investigator's IRB/IEC/IBC for approval before subjects can be enrolled into an amended protocol.

13.2.2 Protocol Deviations

A deviation from the protocol is a departure from the written procedures or processes. A significant deviation occurs when there is nonadherence to the protocol by the subject or investigator that results in a significant, additional risk to the subject. Significant deviations can include nonadherence to inclusion or exclusion criteria, enrollment of the subject without prior sponsor approval, or nonadherence to FDA regulations or ICH GCP guidelines, and will lead to the subject being withdrawn from the study ([Section 7.1](#)). Protocol waivers or exemptions are not permitted. Adherence to the study design requirements, including those specified in the Schedules of Events ([Table 15–1](#) and [Table 15–2](#)), is essential for study conduct.

The investigator or designee must document and explain in the subject's source documentation any deviation from the approved protocol. The investigator may implement a deviation from, or a change of, the protocol to eliminate an immediate hazard to study subjects without prior IRB/IEC/IBC approval. As soon as possible after such an occurrence, the implemented deviation or change, the reasons for it, and any proposed protocol amendments should be submitted to the IRB/IEC/IBC for review and approval, to the sponsor for agreement, and to the regulatory authorities, if required.

Protocol deviations will be documented by the clinical monitor throughout the course of monitoring visits. Principal investigators will be notified in writing by the monitor of deviations. The IRB/IEC/IBC should be notified of all protocol deviations in a timely manner, as required.

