3.1 Study Overview

Study 101HEMB01 is a Phase I/II, open-label, single-arm, multicenter, dose-finding safety study to determine the safety, tolerability, and efficacy of DTX101 in adults with moderate/severe to severe hemophilia B. The primary objectives of the study are to determine the safety of single ascending IV doses of DTX101 and to identify the OBD of DTX101 that either achieves or is the closest to achieving the target peak FIX activity of $\geq 20\%$ of normal.

Eligible subjects will receive a single IV infusion of DTX101. Subjects will be dosed sequentially in cohorts with a minimum of 3 subjects each. Dose escalation will be conducted according to a model that uses safety and efficacy data to predict the OBD ([Section 10.5.1](#)).

The following candidate doses (per kg of body weight) will be used to identify the OBD:

- **Dose 1:** 1.6×10^{12} GC/kg
- **Dose 2:** 3.0×10^{12} GC/kg
- **Dose 3:** 5.0×10^{12} GC/kg
- **Dose 4:** 1.0×10^{13} GC/kg

There will be a minimum of 7 days between dosing of each subject within a cohort and a minimum of 42 days between the dosing of the last subject in one dosing cohort and the first subject in the next dosing cohort. The recommendation to proceed to the next dose cohort will be made by the DSMC ([Section 9.3](#)) after evaluation of the safety data for all subjects in a dosing cohort after they have completed Week 6, as outlined in the DSMC charter. There will be no intra cohort dose escalations.

Study enrollment will be suspended if any of the safety stopping criteria are met ([Section 3.2.4](#)).

Subjects will be followed for 52 weeks after dosing. After completion of this study, subjects will be offered enrollment in an extension study to evaluate the long-term safety and effect of DTX101 on clinical outcome measures.

[figure not shown]

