3.2.5 End of Study

Subjects who complete all visits up to and including the Week 52 visit will have completed the study. Subjects who discontinue early will be asked to return for an Early Withdrawal visit. Subjects with any on-going AEs at this visit will continue to be monitored as outlined in [Section 9.1.5](#). After completion of this study, subjects will be offered enrollment in an

Dimension Therapeutics, Inc

DTX101

Protocol: 101HEMB01 Version 04

03 September 2015

extension study to evaluate the long-term safety and effect of DTX101 on clinical outcome measures.

4 Subject Selection

Subjects will be assigned to study treatment only if they meet all of the inclusion criteria and none of the exclusion criteria.

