9.1 Adverse Events and Serious Adverse Events

Adverse events will be assessed from the time the subject signs the ICF until their exit from the study.

At every study visit, subjects will be asked a standard nonleading question to elicit any medically related changes in their well-being.

In addition to subject observations, AEs identified from any study data (eg, laboratory values, physical examination findings, ECG changes) or identified from review of other documents (eg, subject diaries) that are relevant to subject safety will be documented on the AE page in the eCRF.

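### Protocol 13.2.2 requires withdrawal for any significant deviation, dosed or not, so a breach found after the single infusion ends scheduled follow-up without removing any exposure

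*Protocol*

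**What the plan says.** Protocol 13.2.2 defines a significant deviation as a departure by the subject or the investigator that puts the subject at significant added risk. Its examples are eligibility breaches, enrolling without the sponsor's approval, and departures from FDA regulations or GCP. It states that these can occur "and will lead to the subject being withdrawn from the study", refers to 7.1, and rules out waivers.

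Section 7.1 lists reasons for withdrawal to be recorded. Ineligibility, significant deviation and noncompliance are three separate entries, and none depends on whether the subject has been dosed. Section 7.2 does separate dosed from undosed subjects, but only for replacement: dosed subjects are not replaced.

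On detection, 13.2.2 says "Protocol deviations will be documented by the clinical monitor throughout the course of monitoring visits", and 13.1.1 says "the monitor will visit the investigator and study site at periodic intervals". SAP 4.6.3 has deviations identified before database lock.

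On follow-up:
- Section 3.1: "Subjects will be followed for 52 weeks after dosing".
- Section 3.2.2: the four-weekly visits run to Week 52 or to early withdrawal.
- Section 3.2.5: early leavers are asked to attend an Early Withdrawal visit, and "Subjects with any on-going AEs at this visit will continue to be monitored".
- Section 9.1: "Adverse events will be assessed from the time the subject signs the ICF until their exit from the study".

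**The concern.** For a drug given repeatedly, withdrawal after a serious breach can at least stop further dosing. Here there is one infusion, so once it has been given the rule can only stop observation. It does so in subjects who, by the definition in 13.2.2, carry added risk.

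Safety is a primary objective. The FIX time course and the annualized bleeding rate to Week 52 are secondary endpoints. A dosed subject withdrawn under 13.2.2 stops contributing scheduled chemistry, FIX and bleeding data, and adverse events that begin later are not looked for. Missing values are not imputed (SAP 4.1), so in a minimum-size cohort the by-dose FIX summaries fall from 3 subjects to 2 at later visits.

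The analysis does not need the withdrawal. The Safety Set and As Treated Set keep every dosed subject, and the Per-Protocol Set already removes dosed subjects who have a significant deviation (SAP 4.6.1 to 4.6.3).

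**Working it through.** The plan gives no figure to reproduce here. The check has two parts.

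**Is there an exemption for dosed subjects?** Four places could hold one.
- 13.2.2 separately permits deviations made to remove an immediate hazard. That does not depend on dosing status.
- 7.1 introduces its list with permissive wording, but the list is of reasons to record. It does not make 13.2.2 optional.
- 7.2 concerns replacement only.
- 3.2.4 keeps enrolled subjects under monitoring when enrollment is suspended. That is a study-level event, and the clause itself ends at completion or withdrawal.

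None exempts a dosed subject.

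**What would a withdrawal cost?** Inputs:
- Post-dose clinic visits (Table 15-1): Weeks 2, 4, 6, 8, 10, 12, then 16 to 48 every 4 weeks, then 52. That is 6 + 9 + 1 = 16, each with FIX activity and chemistry.
- Additional clinic or home chemistry (Table 15-2): Days 4, 8, 20, 24, 32, 36, 48, 52, 60, 64, 76 = 11.
- Day 0 post-dose chemistry (Table 15-1, footnote h): 0.5, 4 and 8 hours = 3.
- All post-dose chemistry: 3 + 16 + 11 = 30.
- Chemistry in the 8-week ALT window of 3.2.4 (to Day 56): 3 + Days 4, 8, 14, 20, 24, 28, 32, 36, 42, 48, 52, 56 = 15.

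Withdrawal just after Week 6 (Day 42):
- Weeks lost: 52 − 6 = 46.
- FIX samples lost: 16 − 3 = 13.
- Chemistry lost: 13 clinic + 5 from Table 15-2 (Days 48, 52, 60, 64, 76) = 18.
- ALT-window chemistry lost: Days 48, 52, 56 = 3.

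The Early Withdrawal visit includes FIX activity and chemistry, so it returns one of each. Losses are shown as gross, then net of that visit:

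| Withdrawn just after | Weeks lost of 52 | FIX lost of 16 | Chemistry lost of 30 | ALT-window chemistry lost of 15 |
|---|---|---|---|---|
| Week 2 | 50 | 15, net 14 | 24, net 23 | 9, or 8* |
| Week 6 | 46 | 13, net 12 | 18, net 17 | 3, or 2* |
| Week 12 | 40 | 10, net 9 | 10, net 9 | 0 |
| Week 24 | 28 | 7, net 6 | 7, net 6 | 0 |

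*If the Early Withdrawal visit falls within the 8 weeks.

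The FIX denominator follows Table 15-1. The synopsis can be read as FIX sampling at every visit, roughly every 4 days to Week 12. If all Table 15-2 visits also carried FIX sampling, the Week 6 case would lose 13 + 5 = 18 of 16 + 11 = 27.

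Share of planned follow-up lost to one subject at Week 6:
- 3-subject cohort: 46 / (3 × 52) = 29.5%.
- 12 subjects: 46 / (12 × 52) = 7.4%.
- 18 subjects: 46 / (18 × 52) = 4.9%.

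Withdrawal before Week 6 also loses one of three Week 6 change-from-baseline values in a minimum-size cohort.

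**The case against.** The trigger is narrow. Only deviations that add significant risk count, and two of the three examples in 13.2.2 arise before dosing. A breach identified after Week 52 costs no follow-up. Data already collected stay in the Safety Set and As Treated Set, and ongoing adverse events are still followed. All of this stands and limits the weight of the point. It does not supply an exemption for the dosed subject whose breach is found at a monitoring visit during follow-up.

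A reader might infer more than the documents support:
- **That 13.2.2 contradicts the 52-week follow-up in 3.1.** It does not. Sections 3.2.2, 3.2.5 and 7.1 all provide for early withdrawal, so the 52 weeks are already qualified.
- **That a dose-finding outcome is certainly lost if withdrawal comes before Week 6.** Protocol 10.5.1 models reaching the FIX target within the first 6 weeks, so an earlier value might count; SAP 3.1.2 refers to the level at 6 weeks. Only the loss of the Week 6 change from baseline is clear.
- **That a withdrawn subject is barred from the extension study.** Section 3.1 says "After completion of this study, subjects will be offered enrollment in an extension study to evaluate the long-term safety", and 3.2.5 says "Subjects who complete all visits up to and including the Week 52 visit will have completed the study". Together these suggest that the offer would not cover a withdrawn subject, but the extension study's eligibility rules are not in these documents.
- **That the rule alone leaves late malignancy undetected.** That stopping criterion applies at any time after vector, but scheduled observation in this study ends at Week 52 in any case.

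**Conclusion.** The point holds as a design weakness. As written, 13.2.2 ends scheduled safety and FIX observation in a dosed subject with a significant deviation, removes no exposure by doing so, and is not needed by any analysis set. In the Week 6 illustration the net loss is 12 of 16 FIX and 17 of 30 chemistry samples, with 46 weeks of follow-up.

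This rests on three assumptions: the rule is applied as worded, the breach is found between dosing and Week 52, and FIX is sampled on the Table 15-1 schedule. The timings of withdrawal are illustrative. With no deviation rate in the documents, the expected loss over the whole study cannot be estimated. The change is worth making because it is cheap and the subjects concerned have had a one-time vector infusion.

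**What to change.** Amend 13.2.2 and 7.1 together:
- **Before dosing:** a significant deviation requires withdrawal from the study, as now. The same applies to ineligibility or noncompliance arising from that deviation.
- **After dosing:** such a deviation alone does not end scheduled safety and FIX observation to Week 52.
- **Unchanged:** withdrawal of consent and the remaining 7.1 reasons.

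Both sections need the change. If only the deviation entry were amended, a dosed subject with an eligibility breach could still be withdrawn under the separate ineligibility entry.

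The sponsor should also reconcile whether the prophylaxis washouts in 3.2.3.2 apply to these subjects, because their FIX values cannot be interpreted without that decision.

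The deviation is then handled by Per-Protocol Set exclusion (SAP 4.6.3). The Safety Set and As Treated Set need no change.

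Cost: a short amendment with IRB/IEC/IBC submission (13.2.1), and completion of visits already in the schedule.

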13.3 Study Termination

Although the sponsor has every intention of completing the study, the sponsor reserves the right to discontinue the study at any time for clinical or administrative reasons.

The end of the study is defined as the date on which the last subject completes the last visit (includes follow-up visit).

15.1 Appendix: Schedules of Events

Table 15–1 Schedule of Events – Scheduled Clinic Visits

Procedure	Period	Screening	Dosing	Treatment Period: Week 2 through Week 52 (includes clinic or home visits [see Table 15–2])							Unscheduled	End of Study/Early Withdrawal
	Week	Days –30 to –1	Day 0	2	4	6	8	10	12	16–48 ^a		
	Visit Window (Days)	-	-	±2	±2	±2	±2	±2	±2	±4	-	±7
Informed consent		X										
Demographics		X										
Medical history		X										
Hemophilia history		X										
Prior medication / therapies / procedures		X										
Review of eligibility criteria		X										
FIX genotyping		X										
HLA genotyping		X										
HBV, HCV, and HIV status		X										
FIX inhibitor (Bethesda assay)		X	X ^b			X	X			X ^c	X ^d	X

Procedure	Period	Screening	Dosing	Treatment Period: Week 2 through Week 52 (includes clinic or home visits [see Table 15-2])							Unscheduled	End of Study/Early Withdrawal
	Week	Days -30 to -1	Day 0	2	4	6	8	10	12	16-48 ^a		
	Visit Window (Days)	-	-	±2	±2	±2	±2	±2	±2	±4	-	±7
Coagulation panel (PT/INR, D-dimer assay, aPTT)	X	X ^b	X	X	X	X	X	X	X	X ^d	X	
AAVrh10 neutralizing antibody test (ELISA)	X	X ^b			X	X				X ^c	X ^d	X
Cell-mediated immune response to AAVrh10 and FIX (ELISPOT assay)		X ^b			X	X				X ^c	X ^d	X
AAVrh10 binding antibody IgG assay (ELISA)	X	X ^b			X	X				X ^c	X ^d	X
Saliva, urine, and stool for viral shedding (qPCR) ^f		X ^e	X	X	X	X	X	X	X	X ^d		X
FIX activity (aPTT clot-based assay)	X	X ^b	X	X	X	X	X	X	X	X ^d		X
Hematology / clinical chemistry ^g	X	X ^h	X	X	X	X	X	X	X	X ^d		X
Urinalysis	X		X	X	X	X		X		X ^d		X

Procedure	Period	Screening	Dosing	Treatment Period: Week 2 through Week 52 (includes clinic or home visits [see Table 15-2])							Unscheduled	End of Study/Early Withdrawal
	Week	Days -30 to -1	Day 0	2	4	6	8	10	12	16-48 ^a		
	Visit Window (Days)	-	-	±2	±2	±2	±2	±2	±2	±4	-	±7
12-lead ECG		X	X ⁱ									X
Vital sign measurements (heart rate, blood pressure, respiratory rate)		X	X ^j	X	X	X	X	X	X	X	X	X
Height and weight ^k		X	X ^{b,1}									X ^l
Complete physical examination		X										X
Targeted physical examination ^m			X ^b			X			X	X ⁿ		
AE/SAE monitoring	X	X	X	X	X	X	X	X	X	X	X	X
Concomitant medications / therapies / procedures		X ^b	X	X	X	X	X	X	X	X	X	X
Diary distributed			X									
Diary reviewed				X	X	X	X	X	X	X	X	X
Diary returned												X

Procedure	Period	Screening	Dosing	Treatment Period: Week 2 through Week 52 (includes clinic or home visits [see Table 15-2])							Unscheduled	End of Study/Early Withdrawal
	Week	Days -30 to -1	Day 0	2	4	6	8	10	12	16-48 ^a		
	Visit Window (Days)	-	-	±2	±2	±2	±2	±2	±2	±4	-	±7
Record of spontaneous bleeding episodes		X	X ^b	X	X	X	X	X	X	X	X	X
Record recombinant FIX use		X	X ^b	X	X	X	X	X	X	X	X	X
Prophylactic recombinant FIX washout		X ^o				X ^{p, q}				X ^{r, s}		X ^{r, s}
EQ-5D-5L QoL questionnaire			X ^b							X ⁿ		X
Haem-A-QoL questionnaire			X ^b							X ⁿ		X
DTX101 infusion			X									

Abbreviations: AAVrh10, adeno-associated virus serotype rh10; AE, adverse event; aPPT, activated partial thromboplastin time; ECG, electrocardiogram; ELISA, enzyme-linked immunosorbent assay; ELISPOT, enzyme-linked immunospot; EQ-5D-5L, EuroQoL 5D 5 level; FIX, factor IX; Haem-A-QoL, Haemophilia-Specific Quality of Life; HBV, hepatitis B virus; HCV, hepatitis C virus; HIV, human immunodeficiency virus; HLA, human leukocyte antigen; IgG, immunoglobulin G; INR, international normalized ratio; PT, prothrombin time; QoL, quality of life; qPCR, quantitative polymerase chain reaction; SAE, serious adverse event.

- Following the Week 12 visit, subjects will return to the study site once every 4 weeks starting at Week 16.
- To be collected before DTX101 administration.
- Samples to be obtained at Weeks 16, 32, 40, and 48.

- d. A laboratory parameter may be repeated if there is any concern about the values obtained. Laboratory values must be repeated if ≥ 2 -fold the upper limit of normal or ≤ 0.5 -fold the lower limit of normal.
- e. Saliva and urine samples for viral shedding to be collected before DTX101 administration. Subjects will be provided with an appropriate container to collect a stool sample at home prior to the visit.
- f. Samples for viral shedding to be collected at Weeks 2, 4, 6, 8, 10, and 12 and on Days 8, 20, 36, 48, 64, and 76 (see Table 15-2) until negative on 3 consecutive occasions for each sample matrix.
- g. Hematology to include: complete blood count and differential. Clinical chemistry to include: sodium, potassium, chloride, carbon dioxide, blood urea nitrogen, creatinine, glucose, calcium, phosphate, magnesium, albumin, total protein, creatine kinase, bilirubin (total and indirect), alanine aminotransferase, aspartate aminotransferase, alkaline phosphatase, gamma-glutamyl transferase, and lactate dehydrogenase.
- h. Samples for clinical laboratory assessments to be collected before DTX101 administration and 0.5, 4, and 8 hours after the start of the infusion.
- i. A 12-lead electrocardiogram to be performed in triplicate before the start of infusion. A single 12-lead electrocardiogram to be performed 1 hour after the start of the infusion. The ECGs should be measured with the subject in a semi-supine or supine position, having rested in this position for at least 5 minutes beforehand.
- j. Vital signs to be measured at predose, at 5 minutes after the start of the infusion, and at 0.5, 1, 2, 4, 6, and 8 hours after the start of infusion (± 5 minutes). The predose measurement of heart rate and blood pressure is to be performed in triplicate, with measurements taken 2 minutes apart. Vital signs will also be measured at 22 hours (± 1 hour) after the start of infusion, prior to subject discharge. Vital signs should be measured with the subject in a semi-supine or supine position, having rested in this position for at least 5 minutes beforehand.
- k. Height to be collected at screening only.
- l. Only weight to be collected.
- m. Targeted physical examination to include assessment of the skin and the respiratory, cardiovascular, and gastrointestinal systems.
- n. To be recorded at Weeks 24, 36, and 48.
- o. This is only applicable if a subject does not have a documented history of FIX activity and a baseline sample is needed to confirm severity of hemophilia B. For subjects taking long-acting recombinant FIX prophylactically, washout is to start at Day -28 and last at least 21 days (Day -7). For subjects taking traditional recombinant FIX prophylactically, washout is to start at Day -14 and last at least 7 days (Day -7). The baseline sample must be obtained and results available prior to dosing on Day 0.
- p. For subjects who take long-acting recombinant FIX prophylactically, start washout at Week 3 for the Week 6 FIX measurement.
- q. For subjects who take traditional recombinant FIX prophylactically, start washout at Week 5 for the Week 6 FIX measurement.
- r. For subjects who continue to take long-acting recombinant FIX prophylactically, start washout at Week 21 for the Week 24 FIX measurement and again at Week 49 for the Week 52 FIX measurement.
- s. For subjects who continue to take traditional recombinant FIX prophylactically, start washout at Week 23 for the Week 24 FIX measurement and again at Week 51 for the Week 52 FIX measurement.

Table 15–2 Schedule of Events – Clinic or Home Visits During the Treatment Period

Procedure	Visit Window (Days)	Treatment Period										
		4	8	20	24	32	36	48	52	60	64	76
		± 1	± 1	± 1	± 1	± 1	± 1	± 1	± 1	± 1	± 1	± 1
Clinical chemistry ^{a, b}		X	X	X	X	X	X	X	X	X	X	X
Saliva, urine, and stool for viral shedding (qPCR) ^{c, d}			X	X			X	X			X	X

Abbreviations: qPCR, quantitative polymerase chain reaction.

- Clinical chemistry to include: sodium, potassium, chloride, carbon dioxide, blood urea nitrogen, creatinine, glucose, calcium, phosphate, magnesium, albumin, total protein, creatine kinase, bilirubin (total and indirect), alanine aminotransferase, aspartate aminotransferase, alkaline phosphatase, gamma-glutamyl transferase, and lactate dehydrogenase.
- A laboratory parameter may be repeated if there is any concern about the values obtained. Laboratory values must be repeated if ≥ 2 -fold the upper limit of normal or ≤ 0.5 -fold the lower limit of normal.
- Subjects will be provided with an appropriate container to collect a stool sample at home prior to the visit.
- Samples for viral shedding to be collected at Weeks 2, 4, 6, 8, 10, and 12 (see Table Table 15–1) and on Days 8, 20, 36, 48, 64, and 76 until negative on 3 consecutive occasions for each sample matrix.

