3.2.3.2 Treatment Period

In order to accurately assess vector-derived FIX activity as a result of DTX101 infusion, subjects will stop taking FIX prophylactically prior to the assessment of peak FIX activity at Week 6 and transition to an on-demand regimen for the remainder of the study. Subjects prophylactically using traditional recombinant FIX will be asked to begin the washout period starting at Week 5. Due to the longer half-life, subjects prophylactically taking long-acting recombinant FIX (eg, Alprolix) will be asked to begin the washout period starting at Week 3 ([Figure 3–3](#)).

If, at any time during the study, a subject experiences bleeding episodes frequent enough to consider prophylactic treatment, the investigator will discuss treatment options with the medical monitor. If a subject resumes prophylactic FIX replacement therapy, as rescue treatment after Week 6, additional washout periods prior to Week 24 and Week 52 will also be performed. Subjects prophylactically using traditional recombinant FIX will be asked to begin the washout period starting at Week 23 and Week 51. Due to the longer half-life, subjects taking long-acting recombinant FIX (eg, Alprolix) will be asked to begin the washout period starting at Week 21 and Week 49 (Figure 3–3).

Figure 3–3 Recombinant FIX Washout During the Treatment Period

Abbreviations: FIX, factor IX.

- a. Following washout, subjects will be transitioned to an on-demand regimen for the remainder of the study.
- b. Washout needed if, at any time during the study after Week 6, a subject experiences bleeding episodes frequent enough to consider re-initiating prophylactic treatment.

The on-demand use of recombinant FIX is not prohibited and may be used at any time during the study. Subjects will be asked to record this use as outlined in [Section 8.1.3](#).

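### On-treatment FIX washouts start at a fixed study week but the FIX visits may be early, so the nominal 7- and 21-day washouts can be shortened, mainly at Weeks 24 and 52

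*Protocol*

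**What the plan says.** Protocol Section 3.2.3.2 gives the purpose of the on-treatment washout: an accurate reading of vector-derived FIX activity. It fixes the start by study week. For Week 6, "Subjects prophylactically using traditional recombinant FIX will be asked to begin the washout period starting at Week 5", and at Week 3 for long-acting product. Subjects who resume prophylaxis as rescue after Week 6 also have washouts before Week 24 and Week 52.

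Table 15-1 repeats the start weeks:

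- Footnote p (long-acting): "start washout at Week 3 for the Week 6 FIX measurement".
- Footnote q (traditional): "start washout at Week 5 for the Week 6 FIX measurement".
- Footnote r (long-acting): "start washout at Week 21 for the Week 24 FIX measurement and again at Week 49 for the Week 52 FIX measurement".
- Footnote s (traditional): "start washout at Week 23 for the Week 24 FIX measurement and again at Week 51 for the Week 52 FIX measurement".

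The visit-window row of the same table allows ±2 days at Week 6, ±4 days at Weeks 16 to 48 and ±7 days at end of study. SAP Appendix B labels that last column Week 52 and repeats the windows and footnotes.

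A minimum length is written only for the screening washout, in footnote o (for traditional product, "washout is to start at Day -14 and last at least 7 days (Day -7"). Section 3.2.3.1 describes the same screening washout differently: approximate timing from Day -29, lasting 7 or 21 days, with no floor.

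SAP Section 4.2 says visit windows will be defined but gives none. SAP Section 4.3 asks for an appropriate washout only for the baseline FIX value. SAP Section 11 summarizes FIX activity at each scheduled time point and relates it to dose in a linear mixed-effects model, with no rule for samples drawn after a short washout.

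**The concern.** The washout start is a fixed day and the draw is a movable one. Nothing in the readable text ties the start to the booked visit, sets a minimum on-treatment interval or bars an early draw for a subject in washout. A site can therefore start washout in the named week, hold the visit inside its window, and draw the sample before the nominal interval has passed.

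The clot-based assay cannot separate infused from vector-derived FIX, so the error runs one way: residual product raises the value. At Weeks 24 and 52 the subjects concerned are those who went back on prophylaxis after frequent bleeding. Their readings bear on how long expression lasts, and Week 52 is the study's last scheduled draw. With 12 to 18 subjects in cohorts of about 3, one or two inflated values can change a cohort's time course.

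**Working it through.** **Inputs.** Start weeks from Section 3.2.3.2 and footnotes p to s: 5, 23 and 51 (traditional); 3, 21 and 49 (long-acting). Windows from Table 15-1: 2, 4 and 7 days at Weeks 6, 24 and 52.

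**Day convention.** Week n = Day 7n, counted from Day 0. Merging the Week 2 to 12 visits of Table 15-1 with the days of Table 15-2 then gives Days 4, 8, 14, 20, 24, 28, … 76, 84, with gaps of 4 to 8 days, which fits a schedule of roughly every 4 days.

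**Nominal interval** = 7 × (visit week − start week). Traditional: 7 × (6 − 5) = 7, and likewise 24 − 23 and 52 − 51. Long-acting: 7 × (6 − 3) = 21, and likewise 24 − 21 and 52 − 49. These equal the 7 and 21 days given for screening.

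**Shortest interval** = earliest visit day − start day. **Longest** = latest visit day − start day.

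| Visit | Visit days | Traditional: start, shortest to longest | Long-acting: start, shortest to longest |
|---|---|---|---|
| Week 6 | 40 to 44 | Day 35, 5 to 9 | Day 21, 19 to 23 |
| Week 24 | 164 to 172 | Day 161, 3 to 11 | Day 147, 17 to 25 |
| Week 52 | 357 to 371 | Day 357, 0 to 14 | Day 343, 14 to 28 |

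At Week 52 the window is as long as the whole traditional washout: Day 357 is both the start day and the earliest visit day.

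**Alternative reading.** If Week 51 meant the first day of the 51st week (Day 350), the shortest Week 52 interval for traditional product would be 357 − 350 = 7 days. The nominal intervals would then be 14 and 28 days, which match nothing stated in the documents, so this reading is unlikely.

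**Scale, on assumptions only.** The documents give neither half-lives nor prophylactic doses. Suppose a half-life of 18 to 30 hours (traditional) or 80 to 100 hours (long-acting), and a last dose that raises FIX by 40 percentage points at the start of washout. Residual = 40 × 2^(−hours / half-life).

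| Product | Days since last dose | Residual FIX (points) |
|---|---|---|
| Traditional | 7 (nominal) | 0.1 to 0.8 |
| Traditional | 5 (Week 6 shortest) | 0.4 to 2.5 |
| Traditional | 3 (Week 24 shortest) | 2.5 to 7.6 |
| Long-acting | 21 (nominal) | 0.5 to 1.2 |
| Long-acting | 19 (Week 6 shortest) | 0.8 to 1.7 |
| Long-acting | 17 (Week 24 shortest) | 1.2 to 2.4 |
| Long-acting | 14 (Week 52 shortest) | 2.2 to 3.9 |

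Residuals are proportional to the assumed rise, so a 20-point rise halves them. At 0 days the formula returns the full 40 points, but only if the last dose coincides with the draw. At Week 6 the excess over the nominal residual is at most 2.5 − 0.8 = 1.7 points, against a 20% target.

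**The case against.** **A zero-day draw is not plainly compliant.** A reader might infer that the protocol permits a Week 52 sample with no washout. Section 3.2.3.2 requires a washout before Week 52, and a draw on the day washout begins has none behind it. This stands: the zero marks where the schedule and the text collide, not a sanctioned procedure. The shorter intervals at Week 24, and anything between 0 and 7 days at Week 52, need no such conflict.

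**The 7- and 21-day floor is not a general validity rule.** It appears only in footnote o, for an eligibility sample, and Section 3.2.3.1 words the same washout differently. This stands. The on-treatment benchmark is the nominal interval implied by the start weeks; that it matches the screening lengths supports it but does not make it a stated minimum.

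**The primary endpoint and dose selection are not materially exposed.** A reader might carry the Week 52 figures over to the Week 6 reading that feeds the dose-finding model. At most 2 days are lost there, so the documents do not support that.

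**These are not the only readings off prophylaxis.** After the Week 6 washout all subjects move to on-demand treatment, so subjects who are not rescued are off prophylaxis at every later visit. On-demand FIX may also be used at any time, so no visit is guaranteed free of infused product. Nor do the documents say that rescued subjects have low expression: the trigger is bleeding frequency.

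**Sites may time washout from the booked visit, and Figure 3-3 may label durations.** Both are possible. The figure is not readable here, so the absence of an on-treatment minimum is judged on the text alone.

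**Much of the data already exists.** FIX use is recorded at each scheduled visit and FIX activity is listed by subject. That makes the analysis fix cheap, but no analysis rule yet uses those data.

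**Conclusion.** The concern holds as a mismatch between two scheduling rules. Used together, they can shorten the washout by up to 2 days at Week 6, 4 at Week 24 and 7 at Week 52, leaving 5, 3 and 0 days for traditional product and 19, 17 and 14 for long-acting. This rests on Week n = Day 7n and on the readable text.

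The practical exposure is the secondary FIX time course and the dose-association model at Weeks 24 and 52, only for subjects who resumed prophylaxis after Week 6 and only when the visit is early. Bias in an affected value is upward. Its size cannot be fixed from the documents; the residuals above are illustrations. The point is worth correcting because the correction is cheap and the final durability reading is among those affected. It does not call the Week 6 primary endpoint or the dose choice into question.

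**What to change.** **Protocol and SAP Appendix B.** The sponsor should reconcile footnotes p to s, Section 3.2.3.2 and the visit-window row so that the intended washout has elapsed before the FIX draw. The sponsor should also confirm the intended length, because footnote o (a stated floor, from Day -28 or Day -14) and Section 3.2.3.1 (approximate timing, from Day -29) differ on the screening washout. No washout length or prophylaxis rule is proposed here.

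**SAP Sections 4.2 and 11.** From the FIX-use dates already recorded, derive the time from the last infused FIX to each FIX sample. Flag samples drawn before the intended washout was complete. Show the FIX time course and the dose-association model with and without flagged values. Section 8.1.3 specifies dates for on-demand use, so check that the diary or the concomitant-medication record (Section 6.4) also captures the last prophylactic dose.

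**Cost.** Footnote edits, minor extra programming, and slightly less scheduling freedom for subjects in washout. In reconciling the passages the sponsor will also need to consider how long rescued subjects stay off prophylaxis: under the present windows that already ranges up to 14 days (traditional) or 28 days (long-acting) at Week 52.
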